5.1.3 Secondary End Points

To evaluate the performance of the DIALIVE in patients with ACLF. This is measured by;

Change in Plasma endotoxin level (endotoxin activity and concentration) between;

D1, D3, D5 and D10 across SOC arm $\,$

D1, D3, D5 and D10 across DIALIVE arm

_

¹⁰ In case a patient's treatment is discontinued, the follow up period will remain 28 days from the moment of randomization.

Clinical Investigation Plan	CIP YAQ-002	Version: 7.0 10 October 2019
-----------------------------	-------------	------------------------------

Start and end of a treatment session (on D1, D2 and D3) with DIALIVE D1,D3, D5 and D10 between SOC and DIALIVE arms for patients presenting with the same grades of ACLF (i.e. Grade 1 ALCF compared with Grade 1 ACLF)

Target-Value (TV): 40% reduction; Acceptable-Value (AV): 20% reduction at end of treatment cycle.

• Change in Albumin function (Human non-mercapt albumin -2 (HNA-2) / Human marcapt albumin (HMA) ratio:

D1, D3, D5 and D10 across SOC arm
D1,D3, D5 and D10 across DIALIVE arm
Start and end of a treatment session (on D1, D2, D3) with DIALIVE
D1,D3, D5 and D10 between SOC and DIALIVE arms for patients presenting with the same grades of ACLF (i.e. Grade 1 ALCF compared with Grade 1 ACLF)

TV: 40% reduction; AV: 20% reduction at end of treatment cycle.

- Mortality: 28-days and 90 days
- Change in ACLF Grade
- Change in CLIF-ACLF score
- Improvement in individual organ function: Brain (HE), Kidney (creatinine), CVS (mean arterial pressure), Pulmonary (P/F ratio, or S/F if patient is not intubated), Liver (serum bilirubin) and coagulation (INR and platelets).
- Status at ICU and Hospital Discharge (including discharge to a hospice for palliative care).
- Lengths of stay in ICU and Hospital at D28 and D90
- ICU and Hospital re-admissions with another episode of ACLF up to 3 months after randomisation.

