Primary End Point	To evaluate the safety of the DIALIVE in patients with Acute on chronic liver failure (ACLF)	The percentage of subjects who experience at least one (1) serious adverse event (SAE) between study Day 1 and Day 10; especially the incidence rate of SAE in both arms of the study at Day 1 and Day 10. The percentage of subjects who discontinued DIALIVE due to a serious adverse device event (SADE) between Day 1 (first day of treatment) and Day 10 (DIALIVE arm only).
Secondary End Point(s)	To evaluate the impact of biochemical performance outlined hereunder towards clinical benefit for patients receiving DIALIVE treatment plus Standard of Care vs Standard of Care alone	 Mortality: 28-days and 3 months Change in ACLF Grade Change in CLIF-ACLF score Improvement in individual organ function: brain (HE), kidney (serum creatinine), CVS (mean arterial pressure), pulmonary (P/F ratio or S/F if arterial blood gas info is not available), liver (serum bilirubin) and coagulation (INR and platelet levels). Status of ICU and Hospital Discharge (including discharge to a hospice for palliative care). Lengths of stay in ICU and hospital at D28 and D90. ICU and hospital re-admissions with another episode of ACLF up to 90 days post randomization.

Clinical Investigation Plan	CIP YAQ-002	Version: 7.0 10 October 2019
-----------------------------	-------------	------------------------------

Secondary end	Objectives	Outcomes Measures
Point(s)	To evaluate the performance of the DIALIVE in patients with ACLF	 Change in Plasma endotoxin level (endotoxin activity and endotoxin concentration) between; Study D1,D3, D5 and D10 across SOC arm
		2. Study D1, D3, D5 and D10 across DIALIVE arm
		Start and end of a treatment session with
		DIALIVE on D1, D2 and D3 4. Study D1, D3, D5 and D10 between SOC and DIALIVE arms for patients with the same grade of ACLF at the time of inclusion in the study
		Target-Value (TV): 40% reduction; Acceptable-Value (AV): 20% reduction Change in Albumin function (Human non- mercapt albumin -2 (HNA-2) / Human marcapt albumin (HMA) ratio:
		5. Study D1, D3, D5 and D10 across SOC arm6. Study D1, D3, D5 and D10 across DIALIVE
		arm 7. Start and end of a treatment session with DIALIVE on D1, D2 and D3.
		8. Study D1, D5 and D10 between SOC and DIALIVE arms for patients presenting with the same grades of ACLF
		TV: 40% reduction; AV: 20% reduction

Clinical Investigation Plan CIP YAQ-002 Version: 7.0 10 0	October 2019
---	--------------

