Patients presenting with, or developing during the study period, severe actue renal failure requiring renal support, will receive continuous renal replacement therapy (CRRT) as per standard local practices. This would apply to subjects in both SOC and DIALIVE arms. For those in the DIALIVE arm, the same vascular catheter which is used for DIALIVE treatment may be used for CRRT following the completion of the DIALIVE treatment session. It is however envisaged

that increased intensity of dialysis component in the DIALIVE system (from 1lit/hr to 1.5lit/hr) and allowance for fluid removal in the new protocol may delay or remove altogether the need for CRRTin these situations. The decision for additional CRRT would depend on clinical situation and will be taken by the site PI.

DIALIVE arm consists of standard of care (defined above), plus DIALIVE treatment.

A DIALIVE treatment session denotes treatment for the day, whereas A DIALIVE treatment cycle refers to the total number of treatment days.

A DIALIVE treatment **session** = A minimum, cumulative duration of 8 to 10 hrs (± 30 min) of the DIALIVE treatment, thus allowing for breaks which may be planned (for example patients needing to go for imaging) or unplanned (device clotting, issues with vascular access or other any other unplanned reasons). A break within a treatment session (consisting of a cumulative time longer than 4hrs), or a cumulative duration of less than 8 hrs of dialysis during one day constitutes a session failure for that day. A session failure will require to restart the dialysis session within 24 hrs after the end of the previous session and will reset the start of the dialysis cycle.

A DIALIVE treatment **cycle**= Consists of 3 consecutive days of 8-10 hrs of DIALIVE treatment sessions on each day within the 10 day window period. A break of more than 24hrs between each treatment session will require a new baseline (i.e. a new treatment cycle commenced). A second failed treatment session within the 10 day window period would result in patient exlusion. The patient must have completed one successful treatment cycle within the 10 day window period to be considered evaluable.

Day of randomization constitutes study Day 0.

The first treatment session (DIALIVE arm only) must commence before the end of study Day 1. As such, dialysis might also start on the day of randomization which might created confusion as 'the first day of dialysis' then concurs with DAY 0 of the study schedule.

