5.1.4 Exploratory End points

- To study other exploratory biological and clinical effects of the DIALIVE in patients with ACLF compared with the Standard of Care group. Some of these parameters are centre-specific in line with local expertise, research interest and the capacity to perform these tests. Liver: Changes in MELD score, plasma/serum cCK18/M30 and flCK18/M65 (markers of liver cell death).
- Kidney: Changes in serum creatinine and urinary NGAL (marker of kidney injury).
- Brain: West Haven Criteria to assess changes in severity of hepatic encephalopathy.
- Immune function: Incidence of Infection, changes in white cell count, CRP and assessment of neutrophil and monocyte function.
- Assessment of Coagulation and haemostasis: Incidence of thrombotic or bleeding complications, assessment of proand anti-coagulant clotting factors and complement activation.

Clinical Investigation Plan	CIP YAQ-002	Version: 7.0 10 October 2019
-----------------------------	-------------	------------------------------

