6. STATISTICAL CONSIDERATIONS

An independent statistician will be responsible for all statistical aspects of the investigation.

All statistical analyses will be carried out on the safety population, defined as the subset of randomised patients who receive at least one treatment. No imputation of missing values will be implemented. Only available data will be analysed. In addition, a sensitivity analysis will be carried out to check the main safety results using SAE-data of all evaluable patients, defined as all those patients who received standard of care or those who received the correct dialysis treatment cycle.

Due to the nature of the study all statistical analyses will be descriptive. The categorical variables will be summarised by means of the count and percentages corresponding to each variable category, while continuous variable will be summarised by the mean and Standard Deviation of each distribution or the median and min-max values in case of those variables non-normally distributed.

Clinical Investigation Plan CIP YAQ-002 Version: 7.0 10 October 20	19
--	----

For each treatment arm, treatment-emergent AEs, SAEs, SADEs, ADEs, USADEs and DDs will be summarised by organ system and treatment causality. The number and percentage of patients discontinuing the study due to AEs, SAEs, SADEs or other stopping criteria confirmed by the DSMB (withdrawal of patient consent; development of septic shock; progression to ACLF Grade 3b or more; disseminated Intravascular coagulation; unanticipated serious adverse device effects, device deficiencies, or in the opinion of the PI, the treatment is unsafe to continue) will be summarised by treatment arm.

Secondary and exploratory parameters (changes from baseline at each study visit) will be descriptively analysed by treatment arm by means of the appropriate statistics.

Statistical analyses of safety data will be run when each study cohort is completed (minimally one week FU) and the corresponding results will be communicated to the DSMB.

Special interim data extraction required to comply with the EU ALIVER program.

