Appendix 1b:Chronic Liver Failure Consortium (CLIF-C) Scoring Systems

CLIF-C Organ Failure (CLIF-C OF) Scoring System

Organ System	Score = 1	Score = 2	Score = 3
Liver (mg/dl)	Bilirubin < 6	6 ≤ Bilirubin ≤ 12	Bilirubin >12
Kidney (mg/dl)	Creatinine <2	Creatinine ≥2 <3.5	Creatinine ≥3.5 or renal replacement
Brain (West-Haven)	Grade 0	Grade 1-2	Grade 3-4
Coagulation	INR < 2.0	2.0 ≤ INR < 2.5	INR ≥ 2.5
Circulation	MAP ≥70 mm/Hg	MAP <70 mm/Hg	MAP < 65 mmHg; Vasopressors
Respiratory: PaO2/FiO2 or SpO2/FiO2	>300 >357	≤300 - > 200 >214- ≤357	≤200 ≤214

The shaded areas represent 'Organ Failures'

From: Jalan R, Saliba F, Pavesi M, Amoros A, Moreau R, Gines P, et al. Development and validation of a prognostic score to predict mortality in patients with acute-on-chronic liver failure. Journal of Hepatology 2014; 61: 1038–1047

CLIF-C Acute Decompensation (CLIF-C AD) Formula

10*0.03*Age + 0.66*Ln Creatinine + 1.71*Ln INR + 0.88*Ln WBC +-0.05*Sodium + 8

From: Jalan R, Pavesi M, Saliba F, Amoros A, Fernandez J, Holland-Fischer P, et al. The CLIF Consortium Acute Decompensation score (CLIF-C ADs) for prognosis of hospitalised cirrhotic patients without acute-onchronic liver failure. Journal of Hepatology 2015; 62: 831–840

CLIF-C Acute-on-Chronic Liver Failure (CLIF-C ACLF) Formula

10*[0.33*CLIF-OFs + 0.04*Age + 0.63*Ln WCC - 2]

From: Jalan R, Saliba F, Pavesi M, Amoros A, Moreau R, Gines P, et al. Development and validation of a prognostic score to predict mortality in patients with acute-on-chronic liver failure. Journal of Hepatology 2014: 61: 1038–1047

Clinical Investigation Plan CIP YAQ-002 Version: 7.0 10 0	October 2019
---	--------------

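### Kidney improvement is read from serum creatinine with no distinction for values taken on renal replacement, so a patient started on CRRT can read as improved and one who recovers and stops it can read as worse

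*Protocol*

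**What the plan says.** - **Endpoint.** Section 5.1.3 names the variable: "Improvement in individual organ function: Brain (HE), Kidney (creatinine), CVS (mean arterial pressure". The synopsis agrees: "kidney (serum creatinine". Section 5.1.4 uses creatinine again as an exploratory measure: "Kidney: Changes in serum creatinine and urinary NGAL (marker of kidney injury".
- **Analysis.** Section 6 states: "Secondary and exploratory parameters (changes from baseline at each study visit) will be descriptively analysed by treatment arm". Only available data are used, and nothing is imputed.
- **Renal replacement.** Under section 2.2, patients who present with or develop severe acute renal failure needing renal support "will receive continuous renal replacement therapy (CRRT) as per standard local practices. This would apply to subjects in both SOC and DIALIVE arms". Additional CRRT is decided by the site PI, and the trial is open label (section 5.1).
- **Possible arm difference.** Section 2.2 envisages that the stronger dialysis component of DIALIVE and its "allowance for fluid removal in the new protocol may delay or remove altogether the need for CRRTin these situations".
- **The organ score.** In Appendix 1b, kidney score 3, the highest, is "Creatinine ≥3.5 or renal replacement".
- **Collection.** Section 5.4 schedules the CLIF-C OF score, MELD and clinical laboratory tests at screening and at the assessment visits to Day 28 in both arms.

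**The concern.** CRRT removes creatinine from the blood without any recovery of the kidney. Once a patient is on it, the serum value reflects the machine as well as the organ, and a change from baseline no longer answers whether kidney function improved. The protocol accepts this in Appendix 1b, where renal replacement overrides the creatinine value, but the separate kidney endpoint has no such override. The same patient-visit can be an improvement in one secondary endpoint and the worst kidney category in another.

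The situation is likely to arise. AKI stage 1b is a route into the trial (section 5.3.1), and renal failure alone makes ACLF grade 1 (Appendix 1a). If CRRT use differs between arms, so will the distortion. Less CRRT under DIALIVE would leave more machine-lowered creatinine in the SOC arm and could mask a kidney benefit. More CRRT under DIALIVE could hide harm. MELD, an exploratory endpoint, inherits the problem because its formula in Appendix 3 contains creatinine and no term for renal replacement.

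**Working it through.** The protocol states no figure for this endpoint, so there is none to reproduce. The check compares the rules on possible patient courses, then illustrates how far creatinine can move.

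**1. Same patient, two readings.** The creatinine values are illustrative.

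| Course | Change in creatinine | Appendix 1b kidney score |
|---|---|---|
| Baseline 3.5 mg/dL off CRRT; 2.0 on CRRT | −1.5, i.e. (3.5 − 2.0)/3.5 = 43% fall: reads as improved | 3 to 3: no improvement |
| Baseline 1.2 on CRRT; later 2.0 off CRRT | +0.8: reads as worse | 3 to 2: improved |
| Baseline 1.2 off CRRT; rises to 4.0; 2.0 on CRRT at the visit | +0.8: reads as worse | 1 to 3: worse |

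The first two rows conflict; the third does not. False improvement needs a raised, undialysed baseline, CRRT started later, and a visit value below that baseline.

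**2. Can CRRT alone produce such a fall?** Single-pool model: C(t) = G/K + (C0 − G/K) × exp(−K × t/V). All inputs are assumptions outside the protocol: V = 0.6 × 75 = 45 L, generation G = 0.5 to 1.0 g/day (20.8 to 41.7 mg/h), clearance K = 1.5 to 2.25 L/h, C0 = 4.0 mg/dL (40 mg/L), no residual kidney clearance.

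- Largest 24 h fall (K = 2.25, G = 20.8): G/K = 9.26 mg/L; exp(−1.2) = 0.301; C = 9.26 + 30.74 × 0.301 = 18.5 mg/L = 1.85 mg/dL, 54% lower.
- Smallest 24 h fall (K = 1.5, G = 41.7): G/K = 27.8 mg/L; exp(−0.8) = 0.449; C = 27.8 + 12.2 × 0.449 = 33.3 mg/L = 3.33 mg/dL, 17% lower.
- At 48 h: 1.20 to 3.02 mg/dL, 70% to 24% lower.

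Kidney function is zero throughout, and the Appendix 1b score stays at 3.

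**3. DIALIVE's own clearance.** Section 2.2 runs the dialysis component at 1.5 L/h. The same model at that rate gives a 7 to 15% fall after one 8 h session, and 17 to 36% over 24 h of running time, ignoring rebound between sessions and the separate replacement-fluid component. This lowers creatinine in the DIALIVE arm, whereas more CRRT in SOC would lower it there.

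**4. Effect on an arm mean.** Assume 15 patients with data per arm and a CRRT-related fall of 2 mg/dL each. Then k such patients shift the mean change by k × 2/15: 0.13, 0.27 and 0.53 mg/dL for k = 1, 2 and 4. Both k and the 2 mg/dL are assumptions.

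**5. MELD.** The creatinine term is 9.6 × ln(creatinine). A fall from 3.5 to 2.0 alone lowers MELD by 9.6 × ln(1.75) = 5.4 points.

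**The case against.** The best defence is that the protocol only names the variable. It defines no improvement threshold, does not say that CRRT counts as improvement, and refers to an SAP that could add a rule. Change in ACLF grade and CLIF-C ACLF score, in the same list of endpoints, are built on a score that counts renal replacement as 3. The study is a small, descriptive, first-in-man safety trial without tests.

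Much of this stands, and it limits the point. It does not remove it. The variable and the available-data rule are already fixed, and followed as written they produce a kidney summary that can contradict Appendix 1b.

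Three stronger readings are tempting, and the documents do not support them:

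- **Every patient on CRRT counts as improved.** The third course above reads as worse, and a patient dialysed at entry shows no false fall from starting CRRT.
- **Each such patient adds 1/15 = 6.7 percentage points of false improvement.** That presumes a yes/no responder measure, which the protocol does not define for creatinine, and 15 analysed patients. Fifteen is the evaluable number per arm, whereas the main analysis uses the safety population with available data.
- **The protocol expects less CRRT under DIALIVE, so the endpoint is biased against the device.** The wording is only that treatment "may delay or remove altogether the need for CRRTin these situations". It rests on a dialysis component given within a 10-day window, so it says little about later visits.

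Replacing creatinine with the kidney sub-score would also go too far. Patients who enter with creatinine between 1.5 and 2.0 mg/dL already score 1 and could not improve. A rule that looked only at conventional CRRT would ignore the device's own clearance and favour the DIALIVE arm.

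**Conclusion.** The concern holds as a defect in how one secondary endpoint is read. Creatinine taken on renal replacement is pooled with creatinine taken off it, so the kidney summary can err in either direction for individual patients and can disagree with the protocol's own organ score. The exploratory creatinine and MELD changes share the problem.

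The illustrated falls (17 to 54% at 24 h, 24 to 70% at 48 h) show that an apparent improvement is possible with no kidney function. They rest on assumed kinetics and are not predictions for this trial. The size and net direction of any difference between arms are unknown. The primary safety endpoint, mortality, ACLF grade and CLIF-C ACLF score are not affected in this way. The wording should be corrected, but the trial's main conclusions do not depend on it.

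**What to change.** In section 5.1.3 and the synopsis, keep creatinine and add that a patient-visit on renal replacement counts as kidney failure and not as improved, consistent with Appendix 1b. In the analysis:

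- summarise creatinine and MELD with on-CRRT visits flagged and shown separately;
- report CRRT use by arm and visit;
- present the CLIF-C OF kidney sub-score alongside creatinine, not in its place;
- flag creatinine taken during or soon after DIALIVE sessions in the same way, so that the rule does not favour the DIALIVE arm.

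None of this changes who receives CRRT. Renal replacement status is already needed to score CLIF-C OF at the scheduled visits, so the added burden on sites is small. The cost is slightly more tabulation and fewer creatinine values in the unflagged summary.

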1. OVERALL SYNOPSIS OF THE CLINICAL INVESTIGATION

Title	A multi-centre, randomised controlled study, to evaluate the safety and performance of The DIALIVE Liver Dialysis Device (LDD) in alcohol related cirrhosis patients with Acute on Chronic Liver Failure (ACLF) versus standard of care (SOC).
Study Design	The design is a multi-centre, randomised, controlled, study to generate data for the evaluation of safety (as measured by the percentage of subjects who experience at least one serious adverse event (SAE), and performance (as measured by the lowering of the plasma endotoxin concentrations, and improved albumin function) of the DIALIVE in 30 evaluable patients with Acute on Chronic Liver Failure (ACLF) on the background of alcoholic cirrhosis versus standard of care (SOC).
Hypothesis	The hypothesis is that DIALIVE will significantly improve the prognosis of ACLF patients by modulating systemic inflammation.
Target Population	Men and Women ≥18 years, ≤81yr. Patients with a background of alcoholic cirrhosis who have either: 1. ACLF grade 1, ACLF grade 2 or grade 3a¹ as per CLIF-OF scoring system; OR 2Serum bilirubin > 20 mg/dL (342 µmol/L) as single organ failure²; OR 3. Stage 1b Acute kidney injury³. Treatment will be undertaken in an intensive care (ICU) or renal dialysis unit setting if the patients are randomised to the DIALIVE treatment arm. For patients randomised to the 'Standard of care' arm, the location of treatment (ICU or general ward) will be determined by their clinical need and will be decided by the site Principal Investigator.

_

¹ ACLF grade 3a patients, i.e. with 3 organ failures only, are included based on a favorable safety report by the Data Safety Monitoring Board following review of safety data on 12 ACLF grade 1 and 2 patients studied so far. ACLF grade 1 patients who have poor prognosis (28 day mortality > 15%) according to the more recent evidence, but were not identified within the original CANONIC study.

 $^{^2}$ Rapidly progressive hyperbilirubinaemia with serum bilirubin rising to > 20 mg/dL (342 μ mol/L)in ACLF is associated with high mortality, equivalent to ACLF 1.

 $^{^3}$ Recent data on Acute Kidney Injury (AKI) in decompensated cirrhotics suggest that even milder degrees of renal dysfunction (AKI 1b defined as serum Cr > 1.5 mg/dL or 134 μ mol/L) are associated with high mortality. AKI 1b does not constitute 'kidney failure' in the CLIF-OF scoring system.

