Commencement of DIALIVE treatment session i.e. connection of patient to the Prismaflex machine = time point 0, can occur at any time before the end of study Day 1 subject to availability of all relevant information required for treatment to commence. All blood samples should be measured from this time point. Any pre samples required should be taken just before connection.

Nuts and bolts of DIALIVE Treatment: a ready reference

-Before starting treatment

The patient to be moved to an intensive care unit or similar once randomised to DIALIVE. Appropriate monitoring needs to be instituted including the following:

- Insertion of an arterial line for continuous invasive blood pressure monitoring and blood sampling
- Insertion of a vascular catheter for DIALIVE treatment
- Insertion of a central venous catheter for prompt treatment with vasopressors if required (Lines should be inserted under USS guidance. Correction of clotting abnormalities, if any, should follow local protocols. The line positions should be confirmed through appropriate means; e.g. CXR for neck lines).

 * NB: Majority of ACLF grade 3 patients are likely to be already in the ICU with the above monitoring in situ.

Additional tests (Baseline samples for FBC, U/E, LFT, coagulation, septic screen will already have been collected to check eligibility) prior to commencing DIALIVE therapy will be done:

Arterial blood gas analysis

- Haemolysis screen (FBC including reticulocyte count, blood film, unconjugated and conjugated bilirubin, LDH, haptoglobin, urinary free haemoglobin) – to be performed only on D1, before and after therapy
- DIC screen, if clinically indicated
- And, Endotoxin Activity Assay (EAA) analysis (start of day 1, 2 and 3)
- Blood to be collected as part of biobank samples.(start of day 1, 2 and 3)

Fluid pre-loading of up to 500mls over 1-2 hours is implemented, the volume and speed of fluid therapy to be determined on a clinical basis, and the choice of fluid would preferably be albumin (4.5 or 5% solution as per local availability).

- during dialysis session

- Anticoagulation with unfractionated heparin and/or prostacycline analogues (the dose as per local protocols)
- Blood flow rates on DIALIVE device to be started at 50 mls/min and increased gradually over 1-2 hours to up
 to a maximum of 250 mls/min

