3 RISKS AND BENEFITS OF THE INVESTIGATIONAL DEVICE AND CLINICAL INVESTIGATION

3.1 Anticipated clinical benefits

It is anticipated and hypothesised that a clinically effective Liver Dialysis Device (LDD) could reduce deaths from liver failure, allow earlier discharge from intensive care and in a proportion of patients, prolong survival without transplantation.

Patient groups that could benefit from the device include:

- Patients with ALF and ACLF: preventing need for transplantation or serve as a bridge to transplantation in ALF, and aiding recovery to pre-event level of liver function in ACLF;
- Patients with decompensated cirrhosis who are waiting for a transplant: preventing clinical deterioration while
 on a waiting list thereby reducing mortality;
- Patients with decompensated cirrhosis not considered suitable for transplantation: long term dialysis to improve survival;
- Patients with intractable pruritus and/or fatigue: improve quality of life and prevent need for transplantation.

The following patients may also benefit:

 Multiple organ dysfunction in intensive care – almost all patients with critical illness have endotoxemia which contributes to inflammation;

- Alzheimer's disease and stroke albumin is dysfunctional in these conditions where plasmapheresis has been found to be beneficial;
- Intoxication from protein bound substances protein bound toxins such as drugs and biological weapons may be treatable with albumin exchange;
- Cholestatic syndromes: such as porphyria, in-born errors of metabolism, drug related cholestasis and graft versus host disease;
- Severe iron accumulation treatment of heart failure due to iron overload as albumin can bind iron.

Clinical Investigation Plan CIP YAQ-002 Version: 7.0 10 Octobe	er 2019
--	---------

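### ICU length of stay and ICU discharge status are read as clinical benefit, although allocation sends DIALIVE patients to an intensive care setting and only clinical need sends SOC patients there

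*Protocol*

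**What the plan says.** Section 5.1.3 names "Lengths of stay in ICU and Hospital at D28 and D90" among the secondary endpoints. The synopsis has the same item and also lists "Status of ICU and Hospital Discharge". It puts both under an objective directed "towards clinical benefit for patients receiving DIALIVE treatment plus Standard of Care vs Standard of Care alone". Section 3.1 expects that an effective device could "allow earlier discharge from intensive care".

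Location is set differently in the two arms. The synopsis states for the device arm: "Treatment will be undertaken in an intensive care (ICU) or renal dialysis unit setting if the patients are randomised to the DIALIVE treatment arm". For the SOC arm, "the location of treatment (ICU or general ward) will be determined by their clinical need", as decided by the site investigator. The treatment reference in section 2.2 makes randomisation the trigger: "The patient to be moved to an intensive care unit or similar once randomised to DIALIVE".

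The device setting is not described uniformly. The synopsis allows ICU or a renal dialysis unit, section 2.2 allows ICU or an equivalent, section 2.6 allows HDU or ICU, and the during-treatment schedule in section 5.4 names ICU alone.

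Section 2.2 defines a treatment cycle as three consecutive daily sessions within a 10-day window. It remarks that most ACLF grade 3 patients will probably be in ICU already, and says nothing similar of the other eligible groups (grades 1 and 2, isolated high bilirubin, AKI stage 1b).

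**The concern.** An ICU day can mean two things here. In the SOC arm it means that the patient was ill enough to need the bed. In the DIALIVE arm it may mean only that the device was being delivered there. The protocol does not set aside device-delivery days, does not start the count after the cycle, and does not say how a SOC patient who never enters ICU is counted.

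A plain comparison could therefore show a longer ICU stay with DIALIVE when the clinical course is the same, or hide a real shortening. That bears on the benefit which section 3.1 anticipates.

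ICU discharge status has a related fault. Leaving ICU after the last session can be a protocol event in one arm and is a clinical event in the other. The patients who have such a status at all are also selected differently.

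**Working it through.** The protocol gives no figure for ICU stay and no planning assumption to reproduce. What can be checked is the direction of the shift and how it depends on the unknowns.

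**Inputs from the protocol**
- 15 patients per arm: five cohorts of 3 DIALIVE and 3 SOC (section 5.2), so 5 × 3 = 15.
- Protocol-driven days, *d*: 3 for one uninterrupted cycle. The 10-day window is an outer bound. Section 2.2 excludes a patient after a second failed session, so few patients could approach it.

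**Inputs that are assumptions**
- *p*: share of patients who would need ICU anyway, taken as equal in both arms, with their ICU days covering the treatment days.
- *u*: share of DIALIVE patients treated in ICU proper rather than in an HDU, renal unit or equivalent.

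**Formula.** With no treatment effect, the excess of mean ICU days with DIALIVE is (1 − *p*) × *d* × *u*. The expected number of SOC patients with no ICU stay is 15 × (1 − *p*).

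Worked line: *p* = 0.4, *d* = 3, *u* = 1 gives 0.6 × 3 × 1 = 1.8 days, and 15 × 0.6 = 9 SOC patients with no ICU stay.

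| *p* | Excess days, *d* = 3, *u* = 1 | Excess days, *d* = 3, *u* = 0.5 | Excess days, *d* = 10, *u* = 1 (outer bound) | SOC patients with no ICU stay, of 15 |
|---|---|---|---|---|
| 0.2 | 2.4 | 1.2 | 8 | 12 |
| 0.4 | 1.8 | 0.9 | 6 | 9 |
| 0.6 | 1.2 | 0.6 | 4 | 6 |
| 0.8 | 0.6 | 0.3 | 2 | 3 |
| 1.0 | 0 | 0 | 0 | 0 |

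The shift is zero only if every patient needs ICU anyway (*p* = 1) or no DIALIVE patient is treated in ICU proper (*u* = 0). Otherwise it has one sign.

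For ICU discharge status, take *p* = 0.4 and *u* = 1. All 15 DIALIVE patients have a status, against 15 − 9 = 6 SOC patients. The DIALIVE group then includes patients who did not need ICU, so the two groups are not comparable.

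**The case against.** The strongest reply is that little hangs on this. The study is a first-in-man safety study of 30 evaluable patients, all analyses are descriptive (synopsis and section 6), and section 4.2 leaves efficacy to later trials. No test is invalidated. An analysis plan could also split ICU days. Total ICU days have a legitimate use too: for resource use, days spent delivering the device are a real consequence of the strategy and should be counted. All of this stands. It confines the fault to labelling and interpretation, but the protocol itself fixes both the location rule and the benefit label.

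A reader might infer more than the document supports:
- *That these endpoints measure location and nothing else.* ICU days after the cycle, and the stays of patients who need ICU anyway, still carry clinical information. Because the shift runs against DIALIVE, a shorter stay with DIALIVE would still be informative.
- *That re-admission is distorted in the same way.* Section 5.1.3 and the synopsis limit it to a further ACLF episode, which is a clinical trigger. Hospital stay is not set by the location rule either.
- *That every DIALIVE patient goes to ICU, against a SOC median near 0 days.* The setting may be an HDU, a renal unit or an equivalent, and no share of SOC patients in ICU is stated. A median near 0 needs the assumption that about half or more of them never enter ICU.

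One apparent remedy is also weaker than it looks. Counting ICU days only from Day 11 gives patients who die before then no ICU days, so early death would look like benefit. Appendix 7 reports two DIALIVE deaths within 24 to 36 hours of starting treatment.

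**Conclusion.** The point holds for ICU length of stay and ICU discharge status. The location rules shift the stay comparison towards longer ICU stay with DIALIVE, and nothing in the protocol removes that shift. The direction follows from the text provided some patients do not need ICU and some DIALIVE patients are treated in ICU proper. The size does not follow from the text. For one uninterrupted cycle it is 0.3 to 2.4 mean days over *p* from 0.2 to 0.8 and *u* of 0.5 or 1, all assumed values. The consequence is a misleading descriptive comparison, not an invalid test, and it is worth correcting because the correction is cheap.

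**What to change.** 1. Reconcile the synopsis, sections 2.2 and 2.6 and the section 5.4 schedule on the treatment setting, and state for the endpoint which units count as ICU.
2. In section 5.1.3 and the synopsis, report total ICU days as resource use.
3. For clinical benefit, report ICU days without those from the move for DIALIVE to the end of the last session, in patients not already in ICU at randomisation. Section 7.1.1 says that treatment dates allow session timing to be reconstructed, so no new daily judgement is needed.
4. Count SOC patients never in ICU as 0 days.
5. Interpret ICU discharge status only among patients in ICU for clinical need.
6. Show any Day 11 to Day 28 ICU count only as a supportive summary together with deaths, for example as days alive and out of ICU.
7. Report Day 90 stay only for cohorts 4 and 5, because section 5.3.6 follows cohorts 1 to 3 to Day 28.

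Leave re-admission and hospital stay as they are.

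The cost is endpoint wording and a derivation from dates. A protocol change needs ethical and regulatory approval (section 8), and recruitment was expected to end in December 2019 (section 5.3.8). A new prospective item on the reason for the ICU bed could not cover patients already enrolled and would be an open-label judgement, so recorded dates are the better source. The downside is that DIALIVE patients who would have needed ICU on treatment days anyway lose those days from the benefit count, which favours the device. Both counts should therefore be shown side by side.
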